2.8.1.1 Adverse events of special interest / grouping of AEs

Treatment emergent adverse events by primary system organ class and preferred term

The number and percentage of patients who reported treatment emergent adverse events will be summarized for each primary system organ class and preferred term; overall and by treatment dose form. Primary system organ classes will be sorted alphabetically and, within each primary system organ class, the preferred terms will be sorted in descending order of frequency.

If a patient reported more than one adverse event with the same preferred term, the adverse event will be counted only once at the preferred term level. If a patient reported more than one

adverse event within the same primary system organ class, the patient will be counted only once at the system organ class level.

Treatment emergent adverse events by severity

All treatment emergent adverse events will be summarized with maximum severity for each primary system organ class and preferred term; overall and by treatment dose form. If a patient reports more than one adverse event within the same primary system organ class, only one adverse event will be counted for that patient at the highest severity level in the total row for each primary system organ class. If a patient reported more than one adverse event with the same preferred term, the highest (maximum) severity will be presented.

Treatment emergent adverse events suspected to be related to study drug

An adverse event related to study drug is defined as one considered by the investigator to have a suspected relationship with the diagnostic method or the study drug. The treatment emergent adverse events suspected to be related to the diagnostic method or study drug (according to the investigators) will be summarized by primary system organ class and preferred term; overall and by treatment dose form. Relationship to study drug is considered as suspected for those events where "Relationship to study drug" is answered by the investigator as "Suspected".

Treatment emergent adverse events leading to permanent study drug discontinuation

Treatment emergent adverse events leading to permanent study drug discontinuation will be summarized by primary system organ class and preferred term using; overall and by treatment dose form.

Treatment emergent adverse events requiring action taken with study treatment

Treatment emergent adverse events requiring action to be taken with study treatment will be summarized by primary system organ class and preferred term; overall and by treatment dose form.

Treatment emergent adverse events requiring significant additional medication or therapy

Treatment emergent adverse events requiring significant additional therapy (concomitant medication, non- drug therapy) will be summarized by primary system organ class and preferred term; overall and by treatment dose form.

Treatment emergent adverse events outcome

Treatment emergent adverse events with outcome will be summarized by primary system organ class and preferred term; overall and by treatment dose form.

Treatment emergent serious adverse events

Number and percentage of patients with treatment emergent serious adverse events, regardless of study drug relationship, will be presented by primary system organ class and preferred term; overall and by treatment dose form for safety set.

The patient data listing includes, SOC/PT/Verbatim term, start date/study day, end date/study day, the severity of an AE, whether or not an AE is related to MBW or study drug, and whether or not it is a serious AE, action taken with study drug, outcome, duration. Duration will be calculated as end date – start date+1 and for ongoing last visit date – start date+1.

The following patient data listings will be provided by age group and treatment dose form.

1. Treatment emergent serious adverse event
2. Discontinuation due to treatment emergent adverse events

Additionally, listing of all adverse events and treatment emergent adverse event will be provided for safety set by age group and treatment dose form.

TEAE of special interest

Treatment emergent adverse events of special interest(Elevated BUN and Creatinine, Tinnitus and Hearing loss) will be summarized by primary system organ class and preferred term; overall and by treatment dose form.

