## **7.1 Information to be collected on screening failures**

Patients may discontinue from the study between Visit 1 and prior to start the first intake of antibiotics in context to the study at Visit 2. These patients are considered screening failures.

Only demography data, occurred SAEs and the primary reason for discontinuation (screening failure log) are collected for those patients who fail to enter the treatment phase. It is not necessary to complete all the required evaluations at the time of discontinuation unless medically indicated.

Potential severe adverse events which may have occurred from time of signing informed consent/written assent until screening failure time should be documented in the patient medical records. Reporting during this time period should be followed as described in Section 8.2.

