# **8 Safety monitoring**

## **8.1 Adverse events**

### **8.1.1 Adverse event definition and reporting**

An adverse event is the appearance or worsening of any undesirable sign, symptom, or medical condition occurring after signing of informed consent, even if the event is not considered to be related to the diagnostic method of the study.

Medical conditions/diseases present before first intake of study drug are only considered adverse events if they worsen after study start. Abnormal laboratory values or test results constitute adverse events only if they induce clinical signs or symptoms, require dose reduction or temporary or permanent study drug discontinuation or require therapy. All adverse events with a date of onset up to 30 days following the last dose of study drug/the last study examination must be reported.

The occurrence of adverse events should be sought by non-directive questioning of the patient and his/her parents (for minors) at each visit during the study. Adverse events also may be detected when they are volunteered by the patient during or between visits or through physical examination, laboratory test, or other assessments. All adverse events must be recorded on the Adverse Events CRF with the following information:

1. the severity grade (mild, moderate, severe)
2. its relationship to the study drug(s) (suspected/not suspected)
3. its duration (start and end dates or if continuing at final exam)
4. whether it constitutes a serious adverse event (SAE)

All adverse events should be treated appropriately. Treatment may include one or more of the following: no action taken (i.e. further observation only); study drug or study diagnostic method dosage adjusted/temporarily interrupted; study drug or study diagnostic method permanently discontinued due to this adverse event; concomitant medication given; non-drug therapy given; patient hospitalized/patient's hospitalization prolonged. The action taken to treat the adverse event should be recorded on the Adverse Event CRF.

Once an adverse event is detected, it should be followed until its resolution or until it is judged to be permanent, and assessment should be made at each visit (or more frequently, if necessary) of any changes in severity, seriousness, the suspected relationship to study drug or the diagnostic method, the interventions required to treat it, and the outcome.

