#### **10.5.2 Safety**

Safety assessments will be based mainly on the frequency of adverse events. Adverse events will be coded by primary system organ class and preferred term according to the Medical Dictionary for Regulatory Activities (MedDRA). All AEs will be assigned to the last treatment the patient received before AE start. In the data listings of adverse events, the severity of an AE, whether or not an AE is related to MBW or study drug, and whether or not it is a serious AE, will be indicated. An adverse event related to study drug is defined as one considered by the investigator to have a suspected relationship with the diagnostic method or the study drug. The adverse events will be summarized by the number and percentage of patients in each primary system organ class and preferred term. For summaries by severity of event, the most severe occurrence for a particular preferred term will be used for a given patient. Summary tables of adverse events by treatment and severity will be provided. Multiple occurrences of the same AE or SAE in the same patient in one treatment period will be counted only once, using the worst severity and drug relationship. Data from other tests (e.g. electrocardiogram or vital signs) will be listed, notable values will be flagged, and any other information collected will be listed as appropriate.

Vital signs data will be listed, including change from baseline.

All laboratory data (blood chemistry) will be listed with abnormal values flagged. The laboratory values will be summarized. Incidence of newly occurring or worsening notably abnormal laboratory values will be produced.

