2.2 Analysis sets

In the study protocol, the safety population was predefined as consisting of all patients that enter the study (provide Informed Consent). This was motivated by the fact that the primary focus of this study was not to describe effects of a drug intervention, but to compare the accuracy of two different assessment methods, namely LCI and FEV1. However, a valid assessment of these methods is very difficult in patients without any treatment exposure. Therefore, it was decided to change the definition of the Safety Set

Safety Set: The safety set will consist of all patients that enter the study (provide Informed Consent) and have been exposed to at least one dose of study drug. The Safety set will be used for all analyses.

Table 1-1 Patient classification criteria

Analysis set	Population codes that cause patient to be excluded	Non-PD criteria that cause patient to be excluded
Safety set	1	Did not provide informed consent Did not exposed to at least one dose of study drug

Population code: 0=Include in everything, 1=Exclude from safety set.

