2.8.1 Adverse events (AEs)

The verbatim term recorded on CRF will be identified as adverse event and will be coded by primary system organ class and preferred term using Medical Dictionary for Regulatory Activities (MedDRA) version 18.1 and above, and other version used for coding. Adverse events starting on or after the time of the first inhalation of study drug but not later than 7 days (30 days in the case of a SAE) after the date of last dose of study drug taken or those AE present at baseline with increased severity will be classified as a treatment emergent adverse event and will be included in all summaries. AEs which started and ended prior to baseline and AEs which started prior to baseline but whose severity does not change post baseline will not be included in treatment emergent adverse event.

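### The related-event table pools MBW-related with drug-related events under a study-drug label, the summaries leave out 2 to 3 of the 5 MBW sessions for non-serious events, and SAEs of undosed patients, deaths apart, have no planned output

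*SAP*

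**What the plan says.** **Definition.** Protocol 10.5.2 calls an event drug-related if it is "considered by the investigator to have a suspected relationship with the diagnostic method or the study drug". SAP 2.8.1.1 repeats this: "An adverse event related to study drug is defined as one considered by the investigator to have a suspected relationship with the diagnostic method", with the drug as the alternative cause. One table, overall and by dose form, is to hold both kinds of event.

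**Selection rule.** The same SAP paragraph continues: "Relationship to study drug is considered as suspected for those events where" the investigator has answered that single item as suspected.

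**Recorded causality.** The list of AE CRF contents in Protocol 8.1.1 gives, as item 2, "its relationship to the study drug(s) (suspected/not suspected". Protocol 8.2.2 asks for the relationship to study drug on the SAE form. Yet Protocol 8.1.1 also wants the relationship to drug or diagnostic method reassessed at each visit, and the by-patient listings in Protocol 10.5.2 and SAP 2.8.1.1 are to show "whether or not an AE is related to MBW or study drug".

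**Window.** SAP 2.8.1 counts as treatment-emergent "Adverse events starting on or after the time of the first inhalation of study drug", up to 7 days after the last dose (30 days for an SAE), plus baseline events that worsen. All summaries use these events only.

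**Population.** SAP 2.2 narrows the safety set to patients with at least one dose, and "The Safety set will be used for all analyses". For screening failures, Protocol 7.1 says: "Only demography data, occurred SAEs and the primary reason for discontinuation (screening failure log) are collected".

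**The concern.** MBW is the procedure the study adds, in patients from 6 years of age. Tobramycin is continued routine treatment. A reader of the study report will want to know separately what was attributed to each.

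The planned related-event table cannot tell them. Its heading names the drug, its definition admits the procedure, and its filter reads only the drug item. The display by dose form inherits the mixture.

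The summaries are also tied to dosing, whereas the MBW sessions run from screening to the end of the off-period. Patients who have the screening MBW but are never dosed leave the safety outputs altogether, although their SAEs are collected.

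**Working it through.** No figure in the plan is at issue, so the check sets the rules side by side and compares the visit calendar with the treatment-emergent window.

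**1. An event attributed to MBW only**

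| Investigator's reading of the drug item | Answer | Result in the related-event table |
|---|---|---|
| Follows the SAP/protocol definition | Suspected | Counted under the study-drug heading, in the powder or solution column |
| Follows the item's own label | Not suspected | Left out |

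Neither row yields an MBW-related count. In the second case the event still appears in the general treatment-emergent tables if it falls in the window, but with no attribution to MBW.

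**2. MBW sessions against the window**

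Inputs: visit days from Protocol Table 7-1; window from SAP 2.8.1. Assumption: last dose on day 28, with days 25 to 31 also checked.

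- End of window, non-serious: 28 + 7 = day 35 (range 25 + 7 = 32 to 31 + 7 = 38).
- End of window, SAE: 28 + 30 = day 58 (range 55 to 61).

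| Visit | Day | Non-serious event in window? |
|---|---|---|
| 1 | -26 to -5 | No |
| 2 | 1 | Only if MBW follows the first inhalation |
| 3 | 5 to 9 | Yes |
| 4 | 25 to 28 | Yes |
| 5 | 53 to 56 | No: 53 - 35 = 18 to 56 - 35 = 21 days too late |

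Protocol section 7 lets MBW take place before inhalation or at least 1 hour after it, so Visit 2 can fall either way.

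- Sessions outside: 2 of 5 (40%) if the Visit 2 MBW follows inhalation; 3 of 5 (60%) if it precedes it.
- For 35 patients: 35 × 5 = 175 planned sessions, of which 35 × 2 = 70 to 35 × 3 = 105 are outside.
- Visit 5 would come inside only with a last dose on day 53 - 7 = 46 or later, well beyond the range checked.
- For SAEs, Visit 5 is inside with a last dose on day 28. With a last dose on day 25 the window ends on day 55, so a Visit 5 on day 56 would be outside.

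**3. What happens to events outside the window**

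- *Dosed patients.* SAP 2.8.1.1 promises a listing of all adverse events for the safety set, so whatever is recorded is listed. A non-serious event at Visit 5 is still reportable under the 30-day rule in Protocol 8.4 (to day 58 with a last dose on day 28), and so is listed but not summarised. An event from a pre-dose MBW is summarised only if it is present at baseline and then worsens.
- *Non-serious events before Visit 2.* Protocol 8.1.1 defines adverse events from consent, but Table 7-1 and section 8.2.1 provide only for SAEs before Visit 2. Such events may never be recorded.
- *Undosed patients.* Their SAEs are collected (Protocol 7.1, 8.2.1). They are outside the safety set, and the AE tables and listings are for that set. SAP 2.8.2 lists deaths from the whole database; non-fatal SAEs have no planned output.

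**The case against.** The strongest reply is that the CRF is not among the documents. Protocol 8.1.1, Protocol 10.5.2 and the SAP listing all mention relationship to the diagnostic method or MBW, which fits one field or two. This stands. A reader might infer that only one causality item is recorded; the documents show only that one is specified.

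A reader might also infer that events outside the window vanish and that MBW safety cannot be assessed at all. The all-AE listing answers that for dosed patients, and with 35 planned patients a dated listing is readable. The loss is in the summary tables and for undosed patients.

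Safety of MBW or of the drug is not a stated objective, the protocol describes MBW as non-invasive, and every SAE from consent goes to the sponsor within 24 hours. All true, and these limit the importance: undosed patients' SAEs are missing from the planned outputs, not from oversight.

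The narrower safety set is openly declared in SAP section 4, and a dosed set is proper for treatment-emergent tables. But the reason in SAP 2.2, that the methods are hard to assess without treatment exposure, concerns method evaluation and does not explain leaving out SAEs.

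Finally, no test of adverse events between powder and solution is planned, and both forms share one MBW schedule. A biased comparison between them is not shown; only the labelling of both columns is affected.

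**Conclusion.** The point holds in this form. The definition and the selection rule in SAP 2.8.1.1 conflict, and applying them gives a related-event table that either labels MBW events as drug-related or omits them. This follows from the text whatever the CRF contains, because the rule reads only the drug item.

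For non-serious events, 2 to 3 of 5 MBW sessions lie outside the summaries. This assumes a last dose on day 28 and does not change for days 25 to 31. It is a share of sessions, not of events; the documents give no basis for an expected number of MBW-related events. Counting only the pre-dose sessions would give 1 to 2 of 5, which misses Visit 5.

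Non-fatal SAEs of undosed patients appear in no planned table or listing.

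The documents do not establish that tobramycin-related events will in fact be overstated: that depends on how investigators answer the item. The primary LCI analysis is not affected.

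**What to change.** 1. In Protocol 10.5.2 and SAP 2.8.1.1, remove the diagnostic method from the definition of a study-drug-related event. Present drug-related and MBW-related events in separate tables.
2. State in the SAP which CRF field carries MBW causality. If there is none, add one to the AE and SAE forms and to the list in Protocol 8.1.1.
3. Summarise MBW-related events from consent, as far as collected, to the last visit, independently of the treatment-emergent window.
4. Add a listing of SAEs for all consented patients. Keep the dosed safety set for the treatment-emergent tables.
5. Reconcile the start of adverse event collection between Protocol 8.1.1 and Table 7-1 with section 8.2.1.

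Cost: one extra table and one extra listing. If no MBW field exists, the CRF change may need a protocol amendment. SAP section 4 already refers to dry-run output, so a late field could not fully recover past assessments. The corrected definition and the SAE listing would still be worth having in that case.

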2.8.2 Deaths

All the deaths in the clinical database will be listed with the last dose date/visit, date of death and investigator-reported principal cause by age group and treatment dose form. Treatment emergent adverse event leading to death will be summarized with numbers and percentages; overall and by treatment dose form for safety set.

Laboratory data

Clinical laboratory parameters include creatinine, urea, C Reactive protein, Burkholderia complex, Pseudomonas aeruginosa, Pseudomonas aeruginosa Tobra MIC, blood urea nitrogen (BUN), Choriogonadotropin beta. All laboratory data (Hematology, chemistry and urinalysis) will be summarized for safety set by treatment dose form, overall and visit. For continuous data the summary statistics (number of observations, mean, standard deviation, median, minimum and maximum) will be provided for safety set for both actual value and change from baseline. Visit 2 will be considered as baseline. If baseline value is missing then change is taken from the data recorded at screening. Number and percentage will be provided for categorical data.

Newly occurring or worsening notably abnormal laboratory values to each post-baseline time point will be listed for the selected parameters creatinine (≥ 2 mg/dl, above normal), blood urea nitrogen (BUN) (≥ 40 mg/dl, above normal). A case will be considered as newly occurring if all the components are not clinically notable at baseline but clinically notable thereafter. If patients have a missing baseline value for at least one component, post-baseline values meeting the notable criterion will be considered as newly occurring.

Observed value of all laboratory parameter will be listed with abnormal values flagged (if applicable) for safety set for all patient along with date of assessment, sorted with age group, treatment dose form and visit. A separate listing for pregnancy test (serum and urine) will be provided with date of assessment by age group and treatment dose form for safety set.

2.8.3 Other safety data

2.8.3.1 ECG and cardiac imaging data

Not Applicable.

2.8.3.2 Vital signs

Vital sign including sitting systolic/diastolic blood pressure, sitting radial pulse rate (over a 30 second interval), respiratory rate, body temperature, height, weight, and body mass index (BMI) will be summarized for safety set by descriptive statistics (number of observations, mean, standard deviation, median, minimum and maximum) for both actual value and change from baseline by treatment dose form, overall and visit. If baseline value is missing then change is taken from the data recorded at screening.

Vital signs data will be listed along with date of assessment, sorted with age group, treatment dose form and visit (if applicable), notable values will be flagged(if applicable), and any other information collected will be listed as appropriate.

2.8.3.3 Physical Examination

Not Applicable

2.9 Pharmacokinetic endpoints

Not Applicable

2.10 PD and PK/PD analyses

Not Applicable

2.11 Patient-reported outcomes

Not Applicable

2.12 Biomarkers

Not Applicable

2.13 Other Exploratory analyses

2.13.1.1 Comparisons of change in LCI from baseline to Week 4(Week 0-4) and Week 4 to Week 8 (Week 4-8) between the patients using Tobramycin inhalation powder and patients using Tobramycin inhalation solution

Change in LCI from baseline to Week 4(week 0-4) for patients using Tobramycin inhalation powder and patients using Tobramycin inhalation solution will be calculated as Change=LCI at Week 4 – LCI at baseline. Visit 2 will be considered as baseline. If baseline value is missing then change is taken from the data recorded at screening.

Addition to that, change in LCI from Week 4 to Week 8 (week 4-8) for patients using Tobramycin inhalation powder and patients using Tobramycin inhalation solution will be calculated as change=LCI at Week 8 – LCI at Week 4.

- Summary of LCI at baseline, at Week 4 and at Week 8 will be presented standard descriptive statistics (n, mean, standard deviation, median, minimum and maximum) for both groups.
- The mean change from baseline to Week 4 (week 0-4) and Week 4 to Week 8 (week 4-8) will be estimated for both groups.

Analysis will be done for safety population based on observed data.

2.13.1.2 Comparison of S_{acm} (N2 slope acinar airways) and S_{cond} (N2 slope conductive airways) at baseline and at Visit 4 in patients using Tobramycin inhalation powder vs. patients using Tobramycin inhalation solution.

The S_{acm} and S_{cond} values at baseline and at each post-baseline visit in the patients using Tobramycin inhalation powder and patients using Tobramycin inhalation solution will be summarized by descriptive statistics (n, mean, standard deviation, median, minimum and maximum). Comparison between the patients using Tobramycin inhalation powder and patients using Tobramycin inhalation solution for both parameters i.e. S_{acm} and S_{cond} at baseline and at Visit 4 will be performed using a descriptive statistics.

Additionally, for accessing trend of change in S_{acm} (N2 slope acinar airways) and S_{cond} (N2 slope conductive airways) over time, mean change from baseline over time will be displayed graphically to each respective visit.

Analysis will be done for safety set based on observed data.

2.13.1.3 Comparisons of changes in FEV1 % predicted, CFU and LCI from baseline to visit 3 (Week1)

The change in FEV1 % predicted, CFU and LCI from baseline to Visit 3(Week1) will be calculated using the formula as Change= value at Week 1 – value at baseline. Visit 2 will be considered as baseline. If baseline value is missing then change is taken from the data recorded at screening. Analysis will be performed based on observed data.

- Summary of FEV1 % predicted, CFU and LCI at baseline and at Visit 3(Week1) for both groups will be presented standard descriptive statistics (n, mean, standard deviation, median, minimum and maximum).

- The mean changes in FEV1 % predicted, CFU, and LCI from baseline to visit 3 (week 1) will be displayed for both groups.

Comparisons of changes in FEV1 % predicted, CFU and LCI from baseline to visit 3 will be done based on descriptive statistics. Analysis will be done on safety set.

2.13.1.4 Change in air trapping (FRC_{ples} - FRC_{MBW}) from baseline to Week 1, Week 4 and Week 8.

Air trapping will be assessed by the difference in FRC measured by bodyplethysmography (FRC_{ples}) and FRC measured by MBW (FRC_{MBW}). The air trapping (FRC_{ples} - FRC_{MBW}) and its change from baseline to each post-baseline visit will be summarized by descriptive statistics (n, mean, standard deviation, median, minimum and maximum). The change in air trapping from baseline will be calculated using as Change= Value at post-baseline – value at baseline. Visit 2 will be considered as baseline. If baseline value is missing then change is taken from the data recorded at screening. Analysis will be performed based on observed data for safety set.

